57 insulin degludec for the treatment of patients with diabetes. Insulin degludec, a long-acting basal
58 insulin analog with a half-life of >25 hours and activity of >40 hours^{18,19}, results in comparable
59 glycemic control to glargine¹⁹⁻²¹, but with lower rates of hypoglycemia^{19,20,22}. The efficacy and
60 safety of degludec is well documented in ambulatory patients; however, no studies have assessed
61 the safety and efficacy of these new formulations in the hospital setting. Although we can
62 anticipate a reduced number of hypoglycemic events with insulin degludec, certain features
63 needs to be investigated in the hospital including 1) prolonged duration of action, which may
64 limit the ability to make day-to-day adjustments in insulin dosage; 2) a steady-state insulin
65 concentration achieved after second or third day of therapy^{21,23}; and limited safety data in
66 acutely ill patients with altered nutritional status. Accordingly, the present pilot randomized trial
67 will compare the efficacy and safety of a basal bolus regimen with degludec U100 and glargine
68 U100 in medicine and surgery patients with type 2 diabetes (T2D).

69
70 **Significance and Innovation.** Degludec is a new generation basal insulin analog with a longer
71 duration of action compared to insulin glargine^{18,19}. Several outpatient trials have reported that
72 treatment with degludec results in comparable improvement in HbA1c levels and in lower rates
73 of hypoglycemia compared to glargine U100 insulin. No previous studies; however, have
74 compared the safety and efficacy of the long-acting basal insulin degludec in the inpatient
75 management of patients with diabetes. It is expected that a large number of patients with diabetes
76 will be started or transitioned to this new insulin formulation; so acquiring knowledge on their
77 safety and efficacy is of great clinical interest. Accordingly, the proposed study will provide
78 novel and clinically useful information on the efficacy (BG control) and safety (hypoglycemia)
79 of degludec in the inpatient setting and after hospital discharge in general medicine and surgery
80 patients with T2D.

81

82 **II. SPECIFIC OBJECTIVES:**

83 **Objective 1. To determine differences in inpatient glycemic control, as measured by mean**
84 **daily blood glucose concentration and the frequency of hypoglycemia in general medicine**
85 **and surgery patients with T2D treated with basal bolus regimen with insulin degludec or**

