86 **glargine once daily plus aspart insulin before meals.** We will analyze a total of 180 subjects
87 with T2D treated prior to admission with diet, oral hypoglycemic agents, short-acting GLP1-RA
88 (except long-acting exenatide, dulaglutide and albiglutide), or insulin therapy (except degludec
89 and glargine U300) will be included in this prospective, randomized, open label trial to compare
90 the safety and efficacy of a basal bolus regimen with degludec and glargine in patients with T2D
91 admitted to general medicine and surgery services. Secondary end points include length of stay,
92 hospital complications, and hospital readmissions.

93
94 **Objective 2: To determine differences in glycemic control after hospital discharge between**
95 **treatment with degludec and glargine in medicine and surgery patients T2D.** Patients with
96 poorly controlled diabetes (HbA1c $\geq 7.0\%$) enrolled in Aim 1 will be invited to participate in this
97 open label prospective outpatient study. At hospital discharge, patients will be treated following
98 an HbA1c based algorithm²⁴ for a total duration of the outpatient follow-up of 3 months (see
99 hospital discharge algorithm, page 7).

100

101 **III. RESEARCH DESIGN AND METHODS**

102 **III.A Study Hypothesis (hypotheses):**

103 **Hypothesis #1:** Treatment with degludec and glargine will result in equivalent glycemic control
104 in general medicine and surgery patients with T2D. Degludec will result in lower number of
105 hypoglycemia compared to glargine.

106
107 **Hypothesis:** treatment with degludec and glargine will result in a similar improvement in HbA1c
108 levels after hospital discharge. Degludec will result in lower number of hypoglycemia compared
109 to glargine.

110

111 **III.B Endpoints:**

112 **The primary endpoint** of the trial is non-inferiority in mean differences between treatment groups
113 in their mean blood glucose concentrations during the first 10 days of therapy (non-inferiority
114 will be determined at a difference < 18 mg/dl). All participants who receive ≥ 2 doses of study
115 drug will be included in the analysis.

116

117 **Secondary outcomes** include differences between treatment groups in any of the following
118 measures: Endpoints 1-4 (glycemic control) will be analyzed during the first 10 days of therapy
119 and endpoints 5, 7, 8, and 9 (length of stay and complications) will be analyzed during hospital

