120 stay. Endpoint 6 (readmissions) will be evaluated up to 12 weeks after hospital discharge.

121 1. Proportion of BG readings between 70 mg/dl and 180 mg/dl before meals

122 2. Number of hypoglycemia (< 70 mg/dl and 54 mg/dl) and severe hypoglycemia (< 40 mg/dl)
123 episodes during the first 10 days of therapy in the inpatient setting.

- 124 3. Number of episodes of severe hyperglycemia (BG > 240 mg/dl) after the first day of treatment
125 until the tenth day of therapy
- 126 4. Daily dose of basal insulin, daily dose of prandial insulin, and total daily dose
- 127 5. Length of hospital stay.
- 128 6. Number of readmissions (hospitalization) and Emergency room visits.
- 129 7. Cardiac complications are defined as myocardial infarction, cardiac arrhythmia requiring
130 medical treatment, or cardiac arrest.
- 131 8. Acute kidney injury defined as an increment in serum creatinine ≥ 0.3 mg/dL from baseline or
132 ≥ 1.5 times baseline creatinine (KDIGO) ²⁵.
- 133 9. Hospital mortality.

134

135 III.C Study type:

136 This is a prospective, randomized, open label multicenter trial to compare the safety and efficacy
137 of a basal bolus regimen with degludec and glargine in patients with T2D admitted to general
138 medicine and surgery services.

139

140 This study will include male or female subjects > 18 years. Due to the design of this hospital
141 study, there will be no run-in period. Upon arrival to the emergency department or medical or
142 general surgical wards, subjects will be screened. A total of 180 subjects will be analyzed. A
143 maximum of 108 (60%) surgical or medical patients will be randomized in the study to ensure a
144 balanced proportion of each group is included. Patients with a known history of T2D treated with
145 diet alone, any combination of OADs, short acting GLP-1 RA (liraglutide or exenatide) and
146 insulin prior to admission will be considered potential candidates for this study. Patients treated
147 with degludec, glargine U300 or with long-acting GLP1-RA (dulaglutide, albiglutide and weekly
148 exenatide) prior to admission will be excluded. Patients admitted with acute or chronic medical
149 illnesses, emergency or elective surgical procedures and trauma would be included in the study.

150

151 Insulin therapy will be aimed to maintain fasting and pre-meal blood glucose levels between 100
152 mg/dl and 180 mg/dL while avoiding hypoglycemia. Blood glucose levels between 70 and 100

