- 292 • Research staff will follow the algorithm for outpatient insulin dose adjustment according
- 293 to fasting blood glucose levels (FBG) and/or random blood glucose levels (RBG)
- 294 described below (algorithm for primary care physician).
- 295

296 **During follow up we will collect the following information:**

- 297 1. Glycemic control:
 - 298 a. Mean daily fasting and premeal blood glucose levels
 - 299 b. HBA1C at 1 and 3 months after hospital discharge
 - 300 c. Hypoglycemic events
 - 301 i. A glucose alert value of <70mg/dl.
 - 302 ii. Clinically important hypoglycemia (BG < 54 mg/dl)
 - 303 iii. Severe hypoglycemia, as defined by the ADA, which denotes severe
 - 304 cognitive impairment requiring external assistance for recovery
 - 305 d. Hyperglycemic events (BG > 240 mg/dl)
- 306
- 307 2. Diabetes treatment:
 - 308 a. Number of patients receiving insulin
 - 309 b. Insulin dosage (unit/day)
 - 310 c. Use of oral agents
 - 311 d. Protocol adherence
- 312 3. Clinical Outcome:
 - 313 a. Hospital readmissions
 - 314 b. Emergency room visits
 - 315 c. Postoperative complications
- 316
- 317 4. Management after end of study
 - 318 a. Post treatment telephone call (telephone contact 2 weeks after last clinic visit) to
 - 319 confirm appropriate number of refills and follow up with primary care physician
 - 320 b. Collect information on adverse events post treatment
- 321

322 **Primary care physicians will be provided with the following algorithm for outpatient**
323 **insulin dose adjustment according to fasting blood glucose levels (FBG) or random blood**
324 **glucose levels (RBG)**

Basal Insulin (degludec and glargine)	
If mean FBG > 180 mg/dL for the last 3 consecutive days and no hypoglycemia or no random BG (RBG) <70 mg/dL	Increase daily dose by 4 IU
If mean FBG > 140 mg/dL for the last 3 consecutive days and no hypoglycemia < or	Increase daily dose by 2 IU

no RBG <70 mg/dL	
If mean FBG between 100 – 140 mg/dL and no hypoglycemia or no RBG <70 mg/dL	No Change
If any FBG between 70 – 99 mg/dl	Decrease by 4 IU or 10% of total daily dose
If any FBG or RBG 40- 69 mg/dl	Decrease by 8 IU or 20% of total daily dose
If any FBG or RBG < 40 mg/dl	Decrease total daily dose by 30 – 40%

325
326 For patients discharged on basal bolus, prandial insulin will be adjusted according to
327 postprandial blood glucose levels (PPG) measured 2 hours after the start of the meal.
328

Prandial Insulin (rapid acting insulin)	
PPG < 180	No change

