434 groups will be treated with bolus regimen given half of TDD as basal (degludec or glargine) once
435 daily and half as aspart divided in three equal doses before meals. Patients with poor oral intake
436 or to be kept NPO will receive the basal dose, but prandial dose will be held.¹⁴ Insulin dose will
437 be adjusted daily to maintain a fasting and pre-dinner BG between 80 mg/dl and 180 mg/dl.

439 **Aim 1. Inpatient Arm – Flow Chart**

440

Visit Type	Hosp- Day 1	Hosp- Day 2	Hosp- Day 3	Hosp- Day 4	Hosp- Day 5	Hosp- Day 6	Hosp- Day 7	Hosp- Day 8	Hosp- Day 9	Hosp- Day 10
Visit #	1	2	3	4	5	6	7	8	9	10
Time-days	1	2	3	4	5	6	7	8	9	10
Inf. consent	x									
Inclusion/excl criteria	x									
Randomization	x									
Withdrawal criteria	x	x	x	x	x	x	x	x	x	x
Dose adjustment		x	x	x	x	x	x	x	x	x
Efficacy										
Vital signs	x									x
Phys Exam	x									x
Body weight	x									x

BMI	x									
HbA1c ¹	x									
Fasting BG		x	x	x	x	x	x	x	x	x
Pre-meal BG	x	x	x	x	x	x	x	x	x	x
Safety										
Adv events	x	x	x	x	x	x	x	x	x	x
Hypoglycemia	x	x	x	x	x	x	x	x	x	x
Urine pregnancy test	x									
Trial material										
Drug dispense ²	x									

441 ¹ From medical records if < 3months, order it otherwise after subject has provided consent for study
442 participation.

443 ² As needed

444 **Aim 2. Outpatient Arm – Flow Chart**

445

Visit Type	Discharge Day 1	TC	Clinic visit	TC	TC	TC	Clinic visit	post treatment follow-up
Visit #	1	2	3	4	5	6	7	8
Time-wks ¹	0	2	4	6	8	10	12	14
Inf. consent	x							
Incl/excl criteria	x							
Random	x							
Withdrawal criteria		x	x	x	x	x	x	
Drug Compliance		x	x	x	x	x	x	
Dose adjustment		x	x	x	x	x	x	
Efficacy								
Vital signs	x		x				x	
Phys Exam	x		x				x	
Body wgt	x		x				x	
BMI	x		x				x	
HbA1c			x				x	
Fasting BG	x		x				x	
Safety								
Adv events	x	x	x	x	x	x	x	x
Hypoglycemia	x	x	x	x	x	x	x	x
Urine pregnancy test			x					
Chem, GFR	x		x				x	
Trial material								
Drug dispense	x		x					
Drug account	x		x				x	

446 ¹Telephone calls (TC) and outpatient visits can be completed ±7 days

447

448

449

450 **Assessments for Efficacy**

451 Laboratory measurements will be conducted per standard hospital practices. Samples will be
452 collected and labelled at the clinical research center at each individual institution. Samples will
453 not be stored. Clinical research coordinators and research nurses will obtain data and blood
454 samples to be sent to the central lab at each institution for standard measurements (HbA1c,

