648 randomization and patients will be treated as per study protocol with degludec/glargine as basal
649 bolus regimen with aspart as prandial insulin.

650 After discharge, patients will be treated with glargine or degludec insulin alone or in
651 combination with oral agents according to HbA1c levels.

652

653 **XII. ADVERSE EVENTS:**

654 **Definition:** An adverse event (AE) is any untoward medical occurrence in a subject
655 administered a product, and which does not necessarily have a causal relationship with this
656 treatment. An AE is an unfavorable and unintended sign (including abnormal laboratory
657 findings), symptom or disease temporally associated with the use of a product, whether or not
658 considered related to the product.

659 This includes events from the first trial related activity after the subject has signed the informed
660 consent and until post treatment follow-up period (telephone contact 2 weeks after last study
661 visit).

662 AEs include a clinically significant worsening of a concomitant illness and clinical laboratory
663 adverse event (CLAE). An AE is either a serious AE (SAE) or a non-serious AE.

664

665 The following AEs will be reported as an SAE using the important medical event criterion if no
666 other seriousness criteria are applicable:

- 667 - Suspicion of transmission of infectious agents via the trial product
- 668 - Risk of liver injury defined as alanine aminotransferase (ALT) or aspartate aminotransferase
669 (AST) >3 x UNL and total bilirubin >2 x UNL, where no alternative aetiology exists (Hy's law)
- 670 -Death
- 671 -A life-threatening event in which the subject was at risk of death at the time of the event
- 672 -Inpatient hospitalization and prolongation of existing hospitalization
- 673 -Persistent or significant disability or incapacity
- 674 -Important medical events that may not result in death, or a life threatening event but may
675 require hospitalization
- 676 -Episodes of severe hypoglycemia will be captured as serious AEs.
- 677 - A planned hospitalization for pre-existing condition, or a procedure required by the protocol,
678 without a serious deterioration in health, is not considered to be an SAE.

679
680
681
682
683
684
685
686
687
688
689
690
691
692
693
694
695
696
697
698
699
700
701
702
703
704
705
706
707
708
709
710
711
712
713
714
715
716
717
718
719
720
721
722
723
724

Severity Assessment Definitions:

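### Patients who do not enter Aim 2 have no scheduled contact after hospital, although section XII collects adverse events until a call two weeks after the last visit, so late hypoglycaemia could go unrecorded

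*Combined protocol and SAP*

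**What the plan says.** **Endpoint window.** Secondary outcome 2 in section III.B counts hypoglycaemic "episodes during the first 10 days of therapy in the inpatient setting". Outcome 6 in the same list (readmissions and emergency room visits) is evaluated up to 12 weeks after discharge and is not restricted to Aim 2.

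**Drug action.** The introductory text before section II describes degludec as a basal "insulin analog with a half-life of >25 hours and activity of >40 hours". It lists prolonged action among the features still to be investigated in hospital. It calls the action longer than glargine's ("duration of action compared to insulin glargine") but gives no figure for glargine.

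**Expected direction.** Hypothesis 1 in section III.A reads "Degludec will result in lower number of" hypoglycaemic events.

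**Adverse event window.** Section XII, Definition, runs collection for a subject from informed "consent and until post treatment follow-up period (telephone contact 2 weeks after last study" visit. It records severe hypoglycaemia as a serious adverse event and lists hypoglycaemia among the events needing additional data. Subjects are asked about events at each site visit and telephone contact.

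**Schedules.** In section V, the chart headed "Aim 1. Inpatient Arm – Flow Chart" has columns for hospital Days 1 to 10 and nothing later. The Aim 2 chart beside it has calls and visits from week 2 to week 12 and a post-treatment column at week 14. The follow-up list under Aim 2 in section III.C gives the final contact as "Post treatment telephone call (telephone contact 2 weeks after last clinic visit) to" confirm refills and primary care follow-up. The two-weekly calls are in the same Aim 2 text.

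**The concern.** Aim 2 is by invitation and requires HbA1c of at least 7.0%. Inclusion criterion 2 in section IV sets no HbA1c floor for patients already on oral agents, a short-acting GLP1-RA or insulin; only diet-treated patients need a value above 7.0%. The design can therefore randomise patients who will not be invited to Aim 2. Patients who decline, withdraw or are discontinued as treatment failures join them.

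Staff who follow the Aim 1 chart as written will not contact these patients after they leave hospital. Because section XII gathers events by asking at each contact, hypoglycaemia at home after the last inpatient basal dose would come to light only if the patient volunteered it. The plan wants to learn about prolonged action in hospital patients, yet it schedules no observation of that period for this group. At stake is mainly safety capture. A secondary worry is that missed events might be unequal between arms.

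**Working it through.** **1. The passages side by side**

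| Requirement | Applies to | Scheduled for Aim 1-only patients? |
|---|---|---|
| Adverse events to a call two weeks after last study visit (section XII) | Every subject | No: Aim 1 chart stops at Day 10 |
| Readmissions and emergency visits to 12 weeks (section III.B, outcome 6) | Whole trial | No contact shown |
| Calls every two weeks for 3 months (section III.C, Follow-up Care) | Aim 2 | No |
| Post-treatment call (section III.C, Management after end of study) | Aim 2: timed from a clinic visit, which only Aim 2 has | No |

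The first two rows imply follow-up that the Aim 1 chart does not provide.

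**2. The plan's own figures.** The documents give no figure for late hypoglycaemia. The Aim 1 sample size reproduces and does not depend on this point. With margin 18 mg/dl, SD 45 mg/dl, one-sided alpha 0.05 and power 80%, n = 2 × (45/18)² × (1.645 + 0.842)² = 12.5 × 6.18 ≈ 77.3, so 78 per group. Exact t-test power at 78 is 0.800.

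**3. Drug remaining after the last dose.** At the stated half-life of 25 h, which is a lower bound, the remaining fraction is 2^(−t/25):
- 24 h: 0.514
- 40 h: 0.330
- 48 h: 0.264

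These fractions describe drug, not glucose-lowering effect.

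**4. Illustrative size**

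From the documents: 90 patients per arm; about 10% expected to have inpatient hypoglycaemia (section V, Hypoglycemia), so 9 patients; degludec activity of 40 h, a lower bound.

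Assumed, because the documents give no value:
- stay of L = 3 to 10 days;
- the inpatient hazard continues unchanged after the last dose;
- glargine acts for g = 18 to 36 h;
- a fraction f = 10 to 50% of each arm does not enter Aim 2;
- nothing is observed after the last dose.

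Hazard per hour: h = −ln(0.90)/(24L). Extra patients uncounted on degludec: 90 × f × [exp(−h·g) − exp(−h·40)].

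| Case | L (days) | g (h) | f | Difference in probability | Extra patients of 90 |
|---|---|---|---|---|---|
| Low | 10 | 36 | 10% | 0.0017 | 0.02 |
| Central | 5 | 24 | 30% | 0.0137 | 0.37 |
| High | 3 | 18 | 50% | 0.0309 | 1.39 |

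Against the 9 patients expected per arm, the central case is 0.37/9 ≈ 4% and the high case 1.39/9 ≈ 15%.

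The whole degludec tail, without subtracting glargine, has probability 1 − exp(−40h) = 0.0174, 0.0345 and 0.0569 in the three cases. That is 0.0174 × 9 = 0.16, 0.0345 × 27 = 0.93 and 0.0569 × 45 = 2.56 patients.

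The 40 h runs from the last dose, not from discharge. With once-daily dosing, discharge may come up to about 24 h later, leaving roughly 16 to 40 h of a 40 h action unobserved. The tail figures are therefore maxima for that duration.

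**The case against.** **The inpatient window is a deliberate scope.** Objective 1 concerns inpatient control and Objective 2 the period after discharge. Outcome 2 rests on glucose thresholds measured on the ward. This stands, and outcome 2 need not change.

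**The plan does provide for contact.** A reader might infer from the Aim 1 chart that Aim 1-only patients are to get no post-treatment contact at all. The documents do not support that, because section XII sets a contact for every subject and outcome 6 needs 12-week information. What stands is a contradiction with the schedule: the contact is called for but not placed.

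**Few patients may be affected.** The Aim 2 sample size and the drug supply in section X are planned as if 90 per arm continue. Section XI says, without limiting it to Aim 2, that patients will receive glargine or degludec after discharge according to HbA1c. A figure is missing from the discharge algorithm in the available text. Patients who enter Aim 2 are covered from discharge, under a separate outcome. All this is fair: the number who stop study insulin at discharge is unknown.

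**Unequal loss is an inference.** The documents give no duration of action for glargine and no event rate after discharge. They expect fewer events on degludec and a flatter effect. Section III.C also says that degludec reaches steady state in a period similar to other basal analogs, which fits poorly with assuming a much shorter glargine half-life. More drug remaining need not mean more events.

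**Self-report is weak evidence.** Section X says meters will not be provided, and the trial is open label. Recalled episodes cannot reliably be sorted by glucose threshold. This stands, and is a reason to keep such data apart from outcome 2.

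**Conclusion.** The scheduling gap is real. Section XII and outcome 6 call for information after discharge, and the Aim 1 flow chart schedules no contact to obtain it from randomised patients who do not enter Aim 2. Hypoglycaemia after their last inpatient basal dose could be missed.

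A reader might go further and infer that events are missed more on degludec, so that the hypoglycaemia comparison is biased towards the hypothesis. The documents support only that this is possible. Its size cannot be established from them and is probably small: an excess of about 0.02 to 1.4 patients of 90, about 0.4 in the central case, all resting on an assumed length of stay, hazard, glargine duration and non-entry fraction. Nor does setting 40 h against the length of stay show material bias, because it starts at the last dose, ignores glargine's own tail and applies only to non-entrants.

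The case for change therefore rests on safety capture and internal consistency. The primary endpoint, the sample size and outcome 2 are unaffected.

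**What to change.** 1. Reconcile section XII with the section V chart. Add the telephone contact two weeks after the last study visit to the Aim 1 flow chart for every randomised patient not entering Aim 2. Ask about hypoglycaemia, adverse events, emergency visits and readmissions.
2. For patients withdrawn but still in hospital, obtain the same information by chart review.
3. Pre-specify a period after the last study basal dose and tabulate hypoglycaemia in it by arm, for all randomised patients, as a supportive safety outcome. A period of 48 h is one example; it is a judgement, since about 26% of the drug would remain then at a 25 h half-life. Show self-reported episodes apart from bedside values, and leave outcome 2 as defined.
4. State how outcome 6 is obtained for Aim 1-only patients from week 2 to week 12, which this call does not cover.

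The cost is one call per non-entrant, made by the team already calling Aim 2 patients, plus a chart row and a table. The data will be open-label self-report, recalled at about two weeks and often without meter readings, so they can show that episodes occurred but not support a precise comparison. A call soon after the chosen period would shorten recall, but it would be a new procedure beyond what section XII requires.
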